**Figure 9-1 VX22-864-108 Study Design**

Treatment Period Day 1 to Week 48, VX-864 (N=20)		
Screening Up to 70 days before first dose a	Group B Pretreatment Interval Up to 14 days b before first dose	Group A (n=10) No liver biopsy
		Cohort B1 (n=5) Liver biopsy at Pretreatment Interval and Week 24
		Cohort B2 (n=5) Liver biopsy at Pretreatment Interval and Week 48

n: size of subsample; N: number of subjects

Note: Figure is not drawn to scale.

a In subjects not requiring augmentation therapy washout, the Screening Period will be up to 28 days. In subjects requiring augmentation therapy washout, the Screening Period will be up to 70 days.

b Day -14 to Day -7; pretreatment liver biopsy must be performed at least 7 days before Day 1 dosing.

c There will be no further dosing in this study as of 25 September 2023. All subjects may consent to the posttreatment Telemedicine Visit(s) following final dose of study drug, to monitor for development of AEs of rash (for up to 6 months) and monitor any ongoing AEs of rash (for up to 6 months following resolution of AEs of rash; see Section 9.1.6).

## 9.1.1 Screening

The Screening Period may require multiple visits to complete assessments, and to enable evaluation of eligibility (Table 3-1 and Table 3-2). Please note, there will be no further enrollment of subjects in this study.

[figure not shown]
### 9.1.1.1 Screening for Subjects Who Have Received Augmentation Therapy Within 42 Days Before the Initial Screening Visit

The Screening Period may be up to 70 days in duration (Day -70 through Day -1) for subjects who are discontinuing augmentation therapy. This is to accommodate an appropriate washout of augmentation therapy that is  $\geq 42$  days in duration, enable enough time to perform all required screening assessments which will require multiple visits during screening, and to enable scheduling of the pretreatment liver biopsy (Table 3-1).

Figure 9-2 displays the general recommended order of key screening assessments for subjects who are discontinuing augmentation therapy for subjects screening for enrollment in Groups A or B.

Blood samples will be obtained for antigenic AAT at the initial Screening Visit. If the subject received the last dose of augmentation therapy  $>42$  days prior to sample collection, these results can be used to determine eligibility. If this sample is obtained  $\leq 42$  days after the last dose of augmentation therapy, another sample must be drawn  $>42$  days after the last dose of augmentation therapy to confirm eligibility.

**Figure 9-2 Recommended Order of Key Screening Assessments for Subjects Who Have Received Augmentation Therapy Within 42 Days Before the Initial Screening Visit**

AAT: alpha-1 antitrypsin; β-hCG: beta-human chorionic gonadotropin; FSH: follicle-stimulating hormone; LFT: liver function test

Note: Figure not drawn to scale. **Sites should allow at least 14 days for sample processing and results reporting for level of antigenic AAT and the PiZZ genotype.**

a Safety assessments include height and weight, vital signs, pulse oximetry, physical examination, ECG, FSH, β-hCG, serology, serum chemistry, hematology, coagulation, and urinalysis.

b If serum chemistry (Table 11-2) was completed more than 28 (+7) days before Day 1 dosing, the LFT panel (Table 11-3) must be completed within 28 (+7) days before Day 1 dosing (Section 9.1.1.3).

[figure not shown]
c In Group B only, the pretreatment liver biopsy must be performed at least 7 days before Day 1 dosing, after all eligibility criteria have been met. Local laboratory hematology and coagulation results must be collected and reviewed by investigator within approximately 48 hours prior to the liver biopsy being performed.

### 9.1.1.2 Screening for Subjects Who Have Not Received Augmentation Therapy Within 42 Days Before the Initial Screening Visit

For subjects who were not on augmentation therapy and hence do not require a washout period, the Screening Period will be up to 28 days in duration (Day -28 through Day -1).

Figure 9-3 displays the general recommended order of screening assessments for subjects who are not discontinuing augmentation therapy for subjects screening for enrollment in Groups A or B.

**Figure 9-3 Recommended Order of Screening Assessments for Subjects Who Have Not Received Augmentation Therapy Within 42 Days Before the Initial Screening Visit**

AAT: alpha-1 antitrypsin;  $\beta$ -hCG: beta-human chorionic gonadotropin; FSH: follicle-stimulating hormone; LFT: liver function test

Note: Figure not drawn to scale. **Sites should allow at least 14 days for sample processing and results reporting for level of antigenic AAT and the PiZZ genotype.**

- a Safety assessments include height and weight, vital signs, pulse oximetry, physical examination, ECG, FSH,  $\beta$ -hCG, serology, serum chemistry, hematology, coagulation, and urinalysis.
- b If serum chemistry (Table 11-2) was completed more than 28 (+7) days before Day 1 dosing, the LFT panel (Table 11-3) must be completed within 28 (+7) days before Day 1 dosing (Section 9.1.1.3).
- c In Group B only, the pretreatment liver biopsy must be performed at least 7 days before Day 1 dosing, after all eligibility criteria have been met. Local laboratory hematology and coagulation results must be collected and reviewed by investigator within approximately 48 hours prior to the liver biopsy being performed.

### 9.1.1.3 LFT Panel Before Day 1 Dosing

If serum chemistry (Table 11-2) was completed more than 28 (+7) days before Day 1 dosing, the liver function test (LFT) panel (Table 11-3) must be completed within 28 (+7) days before Day 1 dosing. If an LFT panel is completed, the following results must be met before the subject may proceed to dosing on Day 1:

- ALT and AST  $\leq 2 \times$  ULN
- Total bilirubin  $\leq$  ULN

If the LFT panel results preclude the subject from proceeding to Day 1 dosing, the LFT panel may be repeated every 3 to 4 days until the above criteria are met.

### 9.1.1.4 Repetition of Screening Assessment(s)

Repeating individual screening assessment(s) that did not meet eligibility criteria is not permitted, with the following exceptions:

- If there is clear evidence of a damaged sample, laboratory error, equipment malfunction, or if the investigator believes the result is not consistent with the subject's current medical condition or historic result, collection of a repeat sample for the appropriate laboratory test or assessment may be permitted.
- Spirometry, which may be retested once.
- Exclusionary ALT, AST, GGT, total bilirubin, ALP, INR, platelet, hemoglobin, albumin, or eGFR test results, which may be retested once.

- Exclusionary ECG test results, which may be retested once.
- Screening levels of antigenic AAT performed to determine eligibility may be repeated.

The repeat screening assessment or blood sample may be conducted or drawn, respectively, at the clinic or at home by a qualified visiting nurse, where permitted by local regulations. If repeat values of the individual assessment(s) are within the eligibility criteria and completed within the screening window, then the subject is eligible for the study.

### **9.1.1.5 Rescreening**

Subjects may be rescreened only once for non-safety assessments, except if subject experiences a pulmonary exacerbation (PEx) during the first rescreening, or in the event the clinical site closes or becomes not operational during the first rescreening due to unforeseen reasons (e.g., COVID-19 associated shutdown of site) in which case the subjects may be rescreened more than once. If a subject is rescreened, all screening assessments will be repeated, except for:

- PiZZ genotyping
- Follicle-stimulating hormone (FSH) level (if serum FSH level was in the postmenopausal range as determined by the laboratory performing the test during prior screening)

If a subject is rescreened, a new screening window will begin when the first rescreening assessment has been initiated.

### **9.1.1.6 Extension of the Screening Period**

A subject may have the Screening Period window extended by 2 weeks without medical monitor approval for the following reasons:

- Repetition of Screening Period assessments (Section 9.1.1.4)
- A PEx during the Screening Period
- Unexpected operational or logistic delays, or to meet the eligibility criteria.

Subjects who have not received augmentation therapy within 42 days before the initial Screening Visit may have the Screening Period window extended for an additional 2 weeks (total of 4 weeks extension) with medical monitor approval.

## **9.1.2 Treatment Period**

Treatment Period assessments are listed in Table 3-3 and Table 3-4 (Day 1 through Week 48 Visit).

Completion of study participation is defined in Section 9.1.9.

### **9.1.2.1 Telephone Visits**

For female subjects of childbearing potential only, the result from the urine home pregnancy test kit will be reported by the subject to the study site at these telephone visits.

In subjects who consent to the posttreatment Telemedicine Visit(s), this visit may be conducted as a telephone or video interview, as detailed in Section 9.1.6. Urine pregnancy tests will not be required for these visits.

### **9.1.3        Use of Remote Measures**

The initial Screening Visit and study visits on Day -14 to Day -7 (in Group B only), Day 1, Weeks 24, 48, and Safety Follow-up must be performed in the clinic, even under extenuating circumstances. However, at Screening Visits (other than the initial visit) when the assessments are feasible to conduct in the home setting, and at other study visits as specified in Table 3-3 and Table 3-4 where permitted by local regulations, study assessments may be performed remotely (i.e., home visit). The decision to conduct study visits remotely or in clinic will be at the discretion of the investigator after consultation with the subject.

Early Termination of Treatment (ETT) visit may be performed by telephone or video.

If local regulations or site practice do not allow remote measures, all study visits will be performed in the clinic.

#### **9.1.3.1      Home Health Follow-up Consultation With the Investigator**

Following all home visits, the investigator or qualified designee will review all source documentation associated with the assessments performed at the home visit. The investigator or qualified designee will then engage the subject in a telephone call, telemedicine video conference, or in person within 5 business days after the home visit. This consultation may occur outside the visit window. The home health follow-up consultation with the investigator or qualified designee may include, but is not limited to, verbal confirmation of safety assessments and study compliance information as appropriate. The investigator or qualified designee will follow up on any assessments that were not performed as scheduled. Additional details will be provided in the Study Reference Manual.

### **9.1.4        Safety Follow-up**

The Safety Follow-up Visits are scheduled to occur 14 and 28 ( $\pm$  2) days after the last dose of study drug. The Safety Follow-up Visit assessments are listed in Table 3-4.

The Safety Follow-up Visits are required for all subjects.

### **9.1.5        Early Termination of Treatment**

If a subject prematurely discontinues study treatment, an ETT Visit should be scheduled as soon as possible after the decision to discontinue study drug treatment. Subjects who prematurely discontinue study drug treatment will also be required to complete the Safety Follow-up Visits, approximately 14 and 28 ( $\pm$  2) days after their last dose of study drug.

If the ETT Visit occurs 3 weeks or later following the last dose of study drug, then the ETT Visit will replace the Safety Follow-up Visits, and a separate Safety Follow-up Visit will not be required. The ETT visit may be performed at the site or by telephone or video.

If a subject withdraws consent for the study, no further assessments will be performed. Vertex may retain and continue using the study data and samples after the study ends, and may use the samples and information in the development of the study compound, for other drugs and diagnostics, in publications and presentations, and for education purposes. If a subject withdraws from the study (Section 9.9), the study data and samples collected will remain part of the study.

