**Table 3-3 Study VX22-864-108: Treatment Period, Day 1 through Week 24**

Event/ Assessment a	Treatment Period												Comments	
	Day -14 to Day -7	Day 1	Day 7 ( $\pm 1$ d)	Day 15 ( $\pm 2$ d)	Day 21 ( $\pm 2$ d)	Day 28 ( $\pm 2$ d)	Wk 6 ( $\pm 7$ d)	Wk 8 ( $\pm 7$ d)	Wk 12 ( $\pm 7$ d)	Wk 16 ( $\pm 7$ d)	Wk 20 ( $\pm 7$ d)	Wk 24 ( $\pm 14$ d)	ETT b	
Standard 12-lead ECG		X	X			X			X			X		All ECGs will be performed in triplicate, with subject in supine position after resting for $\geq 5$ minutes. Performed prior to blood draws when on same day. Days 1 and 7: predose and at 3 hours ( $\pm 15$ minutes) postdose Section 11.6.5
Vital signs		X	X	X	X	X	X	X	X	X	X	X		Complete before blood draws after subject has rested for $\geq 5$ minutes. Sections 11.6.3 and 11.6.4
Pulse oximetry		X	X	X	X	X	X	X	X	X	X	X		
Physical examination/ review of symptoms	PE, Group B only	PE	X	X	X	X	X	X	X	X	PE		A complete PE will be conducted on the Pretreatment Interval ( Day -14 to Day -7 ), Day 1 , Week 24 , and ETT Visits; a review of symptoms will be conducted at all other times. If there are any abnormal findings in the review of symptoms, the subject will be instructed to have a complete PE in the clinic. Section 11.6.3	

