**Table 3-4 Study VX22-864-108: Treatment Period, Week 25 through Safety Follow-Up**

Event/ Assessment a	Treatment Period						ETT b	SFU Visits, 14 and 28 (± 2d) Days After Last Dose of Study Drug	Posttreatment Telemedicine Visit(s) c	Comments
	Wk 28 (±7 d)	Wk 32 (±7 d)	Wk 36 (±7 d)	Wk 40 (±7 d)	Wk 44 (±7 d)	Wk 48 (±14 d)				
Study Visit		X		X		X		X		
The Week 48, and Safety Follow-up Visits must occur at the clinic. All other visits may occur at the clinic or at home (if permitted by local regulations) as outlined in Section 9.1.3.
 
If the visit occurs at home, then a home health follow-up consultation with the investigator or qualified designee (i.e., telemedicine video conference, telephone contact, or in person) must be performed within 5 business days after any home visit. The home health follow-up consultation with the investigator or qualified designee can occur outside the visit window, and may also include a separate follow-up with the study coordinator.
 
Section 9.1.3.1

Telephone (or video as appropriate) visit	X		X		X		X		X	
Female subjects of childbearing potential only will report the results of their home pregnancy tests.
 
Section 9.1.2.1
 
Posttreatment Telemedicine Visit(s) to be only conducted in subjects who consent to it. Urine pregnancy testing does not need to be performed during the posttreatment Telemedicine Visit(s).
 
Section 9.1.6

Weight					X		X			Weight will be measured with shoes off.
Standard 12-lead ECG					X		X			All ECGs will be performed in triplicate, with subject in supine position after resting for ≥5 minutes. Performed prior to blood draws when on same day.
										Section 11.6.5

a There will be no further dosing in this study.b ETT Visit may be conducted remotely by telephone or video (Section 9.1.5).

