**Table 3-4 Study VX22-864-108: Treatment Period, Week 25 through Safety Follow-Up**

Event/ Assessment a	Treatment Period						SFU Visits, 14 and 28 ( $\pm$ 2d) Days After Last Dose of Study Drug	Posttreatment Telemedicine Visit(s) c	Comments
	Wk 28 ( $\pm$ 7 d)	Wk 32 ( $\pm$ 7 d)	Wk 36 ( $\pm$ 7 d)	Wk 40 ( $\pm$ 7 d)	Wk 44 ( $\pm$ 7 d)	Wk 48 ( $\pm$ 14 d)			
Vital signs		X		X		X		X	Complete before blood draws after subject has rested for $\geq$ 5 minutes. Sections 11.6.3 and 11.6.4
Pulse oximetry		X		X		X		X	
Physical examination/review of symptoms		X		X		PE		PE	A complete PE will be conducted on Week 48, and SFU Visits; a review of symptoms will be conducted at all other times. If any findings in the review of symptoms are considered abnormal by the investigator, the subject will be instructed to have a complete PE in the clinic. Section 11.6.3
Urine $\beta$ -hCG	Home kit	X	Home kit	X	Home kit	X		X	All female subjects of childbearing potential. Section 11.6.8 At study visits, the urine pregnancy test should be administered and reported by a health professional (e.g., home health nurse, study coordinator). At indicated telephone visits, a urine pregnancy test will be performed with a home kit provided by the study site. Results will be reported to the site by telephone. Section 11.6.2
Serum chemistry		X		X		X		X	Complete before dosing and before biopsy on Week 48 (Cohort B2 only), when applicable. Section 11.6.2
Hematology		X		X		X		X	
Coagulation		X		X		X		X	
Urinalysis						X			Local lab hematology and coagulation results must be collected and reviewed by investigator within approximately 48 hours prior to performing the liver biopsy.
Blood sample for antigenic AAT		X		X		X		X	Section 11.4.1
Blood sample for functional AAT		X		X		X		X	
Blood sample for Z-polymer		X		X		X		X	

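### A late early-termination visit held by telephone can replace the in-clinic Day 28 Safety Follow-up Visit, and its safety assessments are lost

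*Protocol*

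**What the plan says.** Protocol 9.1.4 sets Safety Follow-up at 14 and 28 (±2) days after the last dose and states: "The Safety Follow-up Visits are required for all subjects". Protocol 9.1.3 lists the visits that cannot be remote, ending "and Safety Follow-up must be performed in the clinic, even under extenuating circumstances". The study-visit row of Table 3-4 agrees: "The Week 48, and Safety Follow-up Visits must occur at the clinic".

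Protocol 9.1.5 asks for an ETT Visit as soon as possible after the decision to stop drug, followed by both Safety Follow-up Visits. It then makes an exception: when the ETT is at least three weeks after the last dose, "then the ETT Visit will replace the Safety Follow-up Visits, and a separate Safety Follow-up Visit will not be required". The next sentence reads: "The ETT visit may be performed at the site or by telephone or video". Section 9.1 and the synopsis repeat the rule; the synopsis uses the singular for the visit replaced.

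In Table 3-4 the ETT column is marked only in the telephone/video row. The physical examination comment there says "A complete PE will be conducted on Week 48, and SFU Visits" and does not name ETT. The matching comment in Table 3-3, which begins "A complete PE will be conducted on the Pretreatment Interval", does list ETT among the complete-examination visits.

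The SAP is narrower. Section 7.1 and Table 12-1 note 2 treat a late ETT as replacing the Day 28 visit only, and note 2 maps it to that analysis visit.

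**The concern.** An ETT can be light because two clinic visits normally follow it and collect the safety data. The replacement rule removes what follows without moving its content into the ETT. No text requires a replacing ETT to be in clinic or to include the Safety Follow-up assessments. A site can therefore follow 9.1.5 exactly and close out a subject by telephone, although 9.1.3 does not allow Safety Follow-up itself to be remote under any circumstances.

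What is at stake is the end of the post-dose safety record. Rash is the posttreatment event that the protocol follows specifically (9.1.6), and skin is part of the complete physical examination (11.6.3). Late laboratory changes would be seen only if a sample were taken for another reason. The SAP also leaves open whether such a subject completed the study: 9.2.1 defines completion through the Safety Follow-up or telemedicine visit and does not mention a replacing ETT.

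**Working it through.** There is no sample-size or power figure to reproduce. The check compares the rules with each other and then works through the visit days.

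**1. Mode of visit.** Safety Follow-up: clinic only (9.1.3, 11.1, Table 3-4). ETT: site, telephone or video (9.1.3, 9.1.5, 11.1, Table 3-4 footnote b). Replacing ETT: no separate rule, so the ETT rule applies and remote is allowed.

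**2. Content of visit.** These rows of Table 3-4 are marked at Safety Follow-up and blank at ETT:
- vital signs and pulse oximetry
- physical examination
- serum chemistry, hematology and coagulation
- antigenic AAT, functional AAT and Z-polymer

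Two groups of rows are not counted:
- The urine pregnancy test has the same pattern, but 9.8 and 11.6.2 separately require it every 4 weeks through completion of participation, with home kits.
- ECG and weight could not be placed in their columns with certainty. SAP Table 12-1 has Safety Follow-up visits for both, so leaving them out can only understate the loss.

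The complete physical examination that Table 3-3 names at ETT cannot be done by telephone.

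**3. Which visit the rule can remove.**
- Day 14 window: 14 ± 2 = Days 12-16.
- Day 28 window: 28 ± 2 = Days 26-30.
- Earliest replacing ETT: 3 × 7 = Day 21.
- 21 − 16 = 5, so the rule cannot take effect until at least 5 days after the Day 14 window has closed.

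Despite the plural in 9.1.5, the visit that the rule can waive in advance is Day 28.

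**4. Loss per affected subject, Day 14 attended.** In-clinic follow-up visits fall from 2 to 1. The last scheduled sample is earlier by 26 − 16 = 10 to 30 − 12 = 18 days.

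**5. What reaches the tables.** The treatment-emergent period ends no later than 28 days after the last dose (Protocol 12.3.1, SAP 9.1). Of a Day 28 visit's five window days (26-30), samples on Days 26-28 can enter the SAP 9.4.2 threshold counts, and those on Days 29-30 cannot. Safety Follow-up AAT and Z-polymer values feed only the descriptive follow-up rows.

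**6. Scale.** One subject is 1/20 = 5% of the planned total, or 1/10 = 10% of a group. The documents do not say how many ETT Visits fell on Day 21 or later.

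**The case against.** The strongest reply is that the exception is deliberate and rarely used. Protocol 9.1.3 states the clinic rule and then separately permits a remote ETT. Sections 9.1.9 and 9.9 acknowledge that Safety Follow-up may not be required. The default remains a prompt ETT plus both clinic visits. Adverse events are collected through completion of participation, extra laboratory tests are allowed when clinically appropriate (11.6.2), subjects who met the liver interruption criteria are retested every 3 to 4 days (9.8), and consenting subjects have rash follow-up by telephone or video (9.1.6).

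This shows that replacement is intended. It does not show that losing the assessments is intended. Nor does promptness exclude a late ETT: the instruction to hurry runs from the decision to discontinue, while the three-week rule runs from the last dose. If an interruption under 9.8 later becomes permanent, the ETT can be late even when the site acts at once.

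Some stronger readings are tempting but not supported:

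- **No post-dose samples at all.** A reader might infer from the plural that the rule removes both visits, leaving gaps of 28 + 21 = 49 or 56 + 21 = 77 days since the last on-treatment sample. Day 14 is required by 9.1.4 and 9.1.5, and its window closes before the rule can apply. Missing it is a separate event, and the gaps also assume the worst discontinuation date and no unscheduled sample.
- **The SAP invents Day 28 data.** Note 2 only relabels the visit. Note 4 of the same table treats a visit without a measurement as missing.
- **The threshold table is materially biased.** Any missed draw can leave a subject counted as not meeting a threshold, and samples after Day 28 would not count anyway.

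**Conclusion.** The point holds as a minor gap in safety follow-up. As written, 9.1.5 permits the in-clinic Day 28 visit to be replaced by a telephone call with nothing measured, against 9.1.3, 9.1.4 and Table 3-4. With Day 14 attended, the last scheduled sample moves from Days 26-30 to Days 12-16. The loss is permitted, not certain, because the ETT may also be held at the site.

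The number affected is unknown and probably small. A reader might infer a large number, because dosing stopped for everyone on 25 September 2023 and the SAP reports no post-treatment biopsies. Frequent early termination does not imply that ETT Visits were delayed by 21 days or more, and the documents give no basis for a range. No efficacy estimate changes.

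The conclusion assumes that the ETT column of Table 3-4 is blank for the listed rows. That reading is consistent: the last mark in those rows must be Safety Follow-up, because the only later column is a telemedicine visit.

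**What to change.** **Protocol 9.1.5, 9.1 and the synopsis.** State that an ETT Visit three weeks or more after the last dose replaces only the Day 28 Safety Follow-up Visit, and only if it is held in clinic with the Table 3-4 Safety Follow-up assessments done. Otherwise the in-clinic Day 28 visit is still required, or is held as soon as possible if its window has passed. A make-up visit after Day 28 protects the subject but does not add to the treatment-emergent threshold counts.

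**SAP 9.2.1.** State that a remote ETT is not a completed Safety Follow-up Visit.

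**SAP 9.4.2.** Report beside the threshold table the number of subjects with no laboratory sample after the last dose.

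**SAP Table 12-1 note 2.** Adding the same condition to the mapping is optional, because note 4 already treats unmeasured values as missing.

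**Cost.** One clinic visit per affected subject, already scheduled for everyone under 9.1.4, and a short amendment under Protocol 13.2.4. For a last dose no later than 25 September 2023, the Day 28 window closes by about 25 October 2023 (30 days on). If the windows have passed and late visits are no longer useful, the two SAP changes can be made alone and need no new data.
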